The target population of our study will be comprised of patients that are 18 years-old and above that present to our group at the McGovern Medical School at UTHealth and will require thoracoabdominal incision for the descending/thoracoabdominal aortic aneurysm repair. Our plan is to enroll 20 patients over a period of 6 months.

Inclusion/Exclusion Criteria

Patients will be eligible for the study if:

- 18 years-old or older, and
- Descending/thoracoabdominal incision is planned
- There is reasonable expectation that the patient will be extubated within 48 hours after surgery

Patients will be excluded from the study if:

- The patient has a known allergy to morphine or any opioid
- The patient has a known chronic pain disorder or takes daily opioid medication > 1 month prior to surgery
- The surgeon/anesthesiologist concludes that the period for intubation will be likely be for more than 48 hours after surgery There is anticipated difficulty communicating pain status due to language or other barriers at the investigator discretion.

Protocol Deviation:

It will be considered a protocol deviation if patients receive, during the first three days after surgery, any type of analgesic other than opioids.

Withdrawal criteria:

- Voluntary: patients who had consented and enrolled in the trial will maintain their right to withdraw at any point during the study as explained in the informed consent.
- In case of unexpected/unpredicted

X. STUDY DRUGS

CryoICE® CRYO2 cryoablation probe (AtriCure, Inc) is an FDA-approved device for the use of intercostal nerve cryoablation. Subjects will be randomized into two groups: Group A will receive the study procedure, intercostal nerve cryoablation using CryoICE® CRYO2 cryoablation probes (AtriCure, Inc) to intercostal spaces 4th to 10th in thoracoabdominal aortic repairs and 4th to 8th in descending thoracic aortic repair cases. This procedure will be performed under electromyography to confirm the successful ablation of the nerve. Group B will not receive cryoablation but will obtain electromyography to evaluate as the control.

Both patient groups will receive intraoperative local analgesia infiltration with bupivacaine liposomal injectable suspension (Exparel®, Pacira Pharmaceuticals) and patient-controlled analgesia (PCA) postoperatively.

XI. STUDY SCHEDULE

Expected start date: Jan 1st, 2019

Expected end-date for enrollment: June 30th, 2019

Length of enrollment for each patient: 6 months

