Length of follow-up for each patient: 6 months

Expected end-date of study: January 31st, 2020

XII. STUDY DESIGN/METHODOLOGY

This will be a single institution, prospective, single-blinded, randomized, controlled effectiveness study with 2-armed parallel-group sequential design to assess the efficacy of intraoperative intercostal nerve cryoablation in postoperative pain control when compared to our current standard care, local anesthesia infiltration of Exparel®.

Screened patients meeting the eligibility criteria will be randomized into one of the two study groups. Both patient groups will receive intraoperative local analgesia infiltration with Exparel® prior to wound closure and patient-controlled analgesia (PCA) postoperatively. Each patient will choose whether or not they will use PCA. The first group (A) of patients will receive intraoperative intercostal nerve cryoablation using CryoICE® CRYO2 cryoablation probes (AtriCure, Inc) to intercostal spaces 4th to 10th in thoracoabdominal aortic repairs and 4th to 8th in descending thoracic aortic repair cases prior to wound closure. This procedure will be performed under electromyography to confirm the successful ablation of the nerve. The second group (B) of patients will be injected with Exparel® in the surgical wound. We will obtain intraoperative electromyography to evaluate as the control.

On the screening visit, patients should present prior to surgery to receive training on the NPS and BPI and to be assessed on their preoperative baseline pain level, using BPI. This may be performed prior to surgery in the preoperative holding area, on the inpatient ward, or in the outpatient settings of the McGovern Medical School at UTHealth.

Patients from both groups will receive the same volume of diluted Exparel®, which will be given in four 20ml syringes using 22-gauge needles (266mg of liposomal bupivacaine, equivalent of one 1.3% 20ml vial of EXPAREL, diluted in 50ml of preservative-free normal (0.9%) sterile saline for a total volume of 70ml). Intercostal muscle electromyogram will be performed in both groups. Group A will have it done before and after the cryoablation. This assessment is to confirm the completeness of the intercostal nerve cryoablation, as the waveform of the electromyogram is expected to disappear after an adequate cryoablation. Group B will have the electromyogram prior to wound closure. The surgical wound length will

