be measured. Patients will be injected according to the surgical incision required. Patients that require thoracotomies or thoracoabdominal incisions will undergo serial intercostal nerve blocks. Intercostal nerve block will be done injecting 10 cc (of the total 70cc) on each side of the incision, from two above to two below the incision (total 50 cc for intercostal nerve block). In addition, all patients (including all surgical incisions) will be injected in the fascia, subcutaneous tissues, periosteum (if applicable) and parietal pleura (if applicable). The total volume injected will be 70cc regardless of incision type.

All patients will be blinded to having the cryoablation or not. The surgical team will be blinded up only until the time of wound closure as the knowledge of cryoablation is inevitable.

Patients will have access to the standard PCA (Patient-Controlled Analgesia) offered at the Memorial Hermann Hospital – Texas Medical Center. The PCA drug will be Dilaudid (hydromorphone). Initial dosing will be per the standard hospital protocol of 0.2 mg demand dose, 10-minute lockout, 2 mg per hour max, 0.4 mg rescue dose. Adjustments to the PCA dosing will be made based on clinical needs. Patients will receive PCA until the third postoperative day, and at that point, PCA will be switched to an oral analgesic, at the health-care team discretion. Modifications to the PCA regimen can be made by the health care team based on clinical need and will not be deemed a protocol deviation.

Pain assessment should start just after the patient is extubated and can adequately evaluate his/her own pain through the Numeric Pain Scale. NPS will be repeated and recorded at: twice daily (AM and PM) during the third and fifth post-operative day. NPS will also be done right before the first opioid rescue medication postoperatively (if applicable and if NPS had not been assessed within the last hour).

Patients in the study should also complete the Brief Pain Inventory (BPI) before the procedure, at (+/- 2 hours) of the during the third and fifth post-operative day, as well as on their 30th and 180th post-operative days. Patients will be assessed on their satisfaction with the postsurgical analgesia. This will be done using the 5-point satisfaction scale with 1 being “very dissatisfied” to 5 being “very satisfied” at

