will be presented in an easy to comprehend questionnaire for the patients to quantify and communicate their pain experience and how it is affecting their life. It is designed such that patients with 6th-grade education should be able to complete the questionnaire on their own. Question and answers will be provided in a check-box format. The BPI that will be used on this study will be the short version. Patients with difficulty reading or who are physically unable to complete the questionnaire will be assisted by the research team based on their verbal responses to the BPI questions.

4. Enrollment

After the screening is done, the eligibility criteria are met, and the patient is consented; the patient will be enrolled in the trial. At this point, the study coordinator/research office will be notified so that the patient can be randomly allocated to one of the study groups.

5. Randomization and Allocation Concealment

Randomization and allocation concealment will be performed via a web-based/computer generated block randomization sequence/list secured in a password-protected secure computer in the trial office accessible only to the research staff independent of the trial administration process, who are not involved in the recruitment, data collection, analysis, assessment and/or follow-up. This office/research staff will be contacted by the blinded research assistant/investigator to provide certain specific

6. Preoperative assessment

Pain assessment will be also done using the BPI form.

7. Follow-up

After the surgical procedure is done, the follow-up will be:

- i. 7am (+ or - 2 hours) of the third post-op day: the NPS and the the BPI and 5 -point scale analgesia satisfaction survey will be assessed
- ii. 7pm (+ or - 2 hours) of the third post-op day: the NPS will be assessed
- iii. 7am (+ or - 2 hours) of the fourth post-op day: the NPS and the the BPI and 5 -point scale analgesia satisfaction survey will be assessed
- iv. 7pm (+ or - 2 hours) of the third post-op day: the NPS will be assessed

- v. 7am (+ or - 2 hours) of the fifth post-op day: the NPS and the the BPI and 5-point scale analgesia satisfaction survey will be assessed
- vi. 7pm (+ or - 2 hours) of the fifth post-op day: the NPS will be assessed
- vii. 30 days after the procedure, the BPI and 5-point scale analgesia satisfaction survey will be assessed.
- xiii. Final visit, 180 days after procedure, the BPI and 5-point scale analgesia satisfaction survey will be performed.

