Although the study is designed as a pilot trial to collect preliminary data for assessment of feasibility, the proposed sample size of 20 subjects would be large enough to detect a seven point decrease (from 21 to 14) in the cumulative three-day postoperative BPI, with 80% power at alpha <0.05. This would equate to an average reduction of roughly two points per day in the 10-point pain scale over three postoperative days, or about a 1/3 reduction in total pain during that period with cryoablation compared to the control treatment. These estimates are based on prior work by our group with a randomized trial of injectable liposomal bupivacaine (the control treatment in this trial). This would be a large effect, but certainly within the realm of feasibility.

XV. ETHICS

A. Informed Consent Process

All eligible patients who meet the inclusion criteria will be consented, if willing, after an in-depth description of the study, the study drug and its adverse effects, the risks and benefits, follow-up routine, enrollment and termination terms. The importance of follow-

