There is a small increased risk to the patients by participating in the study in addition to a possible chance of breach in patient confidentiality as the study involves evaluation of an FDA-approved device. As detailed in the informed consent, the subjects are at risk of developing adverse effects from cryoablation, abdominal muscle bulging or sympathetic nerve paresis. Patients will be offered standard optimal medical therapy options, even if that will culminate in withdrawal from the study. In addition, there is risk of an unintentional disclosure of personal health information.

Benefits to participants

The patients stand to receive no direct benefit from the study. However, in the event our results endorse the published reports of reduction in postoperative pain by cryoablation, the group of patients receiving it might be indirectly benefitted through participation.

XVI. STUDY TIMELINE

Considering our group's monthly average for the given procedures and the enrollment rates, drop-outs and withdrawal, and interim analyses we estimate recruitment of our sample size will take 6 months. Once the follow-up of all enrolled participants is finished, data will be analyzed and published. The following is a chronological estimate of the stages:

Stage 1: Patient screening and enrollment 0 - 6 months

Stage 2: Follow-up up to 180 days from the last patient enrolled (0 – 12 months)

Stage 3: Data collection and analysis 1 month

Stage 4: Presentation and publication period (at the end of data analysis)

XVII. QUALITY CONTROL AND ASSURANCE

The PI will be responsible for monitoring the progress and safety of this pilot trial. Any serious or unanticipated events will be reported in a timely manner to the CPHS.

XVIII. CONFLICT OF INTEREST

There is no relationship between the principal investigator or any other research staff member and AtriCure Inc. The 10 probes are provided from the AtriCure Inc. for the current study.

XIX. FUTURE PUBLICATION AND PRESENTATION

The results of this study will be analyzed and published after the approval of the principal investigator and biostatistician in a peer-reviewed scientific journal and/or presented at an international/national scientific conference or meeting regardless of outcome. The publication will acknowledge members of the study research group for their contributions and will maintain patient data protection.

XX. REFERENCES

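### Allocation is requested at enrolment although the arms do not diverge until just before wound closure, so losses before closure needlessly cost a 20-patient trial numbers and block balance

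*Combined protocol and SAP*

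**What the plan says.** **Timing of allocation.** Consent is obtained before the operation: in clinic, on admission or in the holding area (XII, Study Conduct item 1; XV.A). Under item 4, once screening, eligibility and consent are complete, the patient is enrolled and the office is told "so that the patient can be randomly allocated to one of the study groups". Item 5 describes a block-randomised list held by independent staff. Its text breaks off before saying when the allocation reaches theatre.

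**Timing of treatment.** Section XII places cryoablation before wound closure in Group A, and for controls "Group B will have the electromyogram prior to wound closure". Both arms receive the same liposomal bupivacaine infiltration and the same access to PCA. On masking, it says "The surgical team will be blinded up only until the time of wound closure".

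**Eligibility.** Section IX requires a reasonable expectation of extubation within 48 hours and excludes a patient if "The surgeon/anesthesiologist concludes that the period for intubation will be likely be for more than 48 hours after surgery". No time is given for that conclusion, and nothing says that it is revisited after enrolment.

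**Losses.** Item 8.iii ends enrolment if any medical, surgical or environmental condition arises that would impair outcome measurement. Section XIV names no analysis set and does not increase the sample size for losses. Section XVI mentions drop-outs only when estimating how long recruitment will take.

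**The concern.** A patient counts as randomised from the moment the allocation is drawn. Here that moment is requested before major aortic surgery, while the first difference in treatment comes at the end of it. Everything that can go wrong in between becomes a post-randomisation loss, although nothing that happened could have depended on the arm.

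Two things are at stake. First, there are only 20 patients, and the power statement leaves no margin. Second, each lost patient has used up a place in a block, so the arms that are actually compared may be uneven. The early draw brings no visible benefit in return, because the allocation is not needed until just before closure.

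**Working it through.** **1. Where losses fall.** Setting the sections side by side gives three intervals.

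- *Enrolment to just before closure.* Arms treated alike, team blinded. Losses here should be unrelated to arm. They cost numbers and block balance, and a later draw turns them into losses before randomisation.
- *At or after closure.* The team knows the arm. Item 8.iii allows removal on judgement, so this is where bias could enter. A later draw does not by itself prevent it.
- *Closure to the day 3 to 5 assessments.* Deaths and actual prolonged intubation still occur, whenever the draw is made.

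**2. The plan's own figure.** Section XIV.C claims that 20 patients detect a fall of 7 points (21 to 14) in cumulative three-day BPI "with 80% power at alpha <0.05". No standard deviation is given; the text says only "These estimates are based on prior work by our group with a randomized trial of injectable liposomal bupivacaine". The figure therefore cannot be reproduced and has to be solved backwards. Assumptions: two-sided 0.05, and 10 per arm (the ratio is not stated; 10 probes for 20 patients, section XVIII, suggests it).

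- Normal approximation: SD = 7 / [√(2/10) × (1.960 + 0.842)] = 7 / 1.253 = 5.59.
- t-test: power 0.80 at 10 v 10 requires d = 1.325, so SD = 7 / 1.325 = 5.28.

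**3. Power after losses.** Power = P(|T| > critical t), where T is noncentral t with n1 + n2 − 2 degrees of freedom and noncentrality d / √(1/n1 + 1/n2), d = 1.325.

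| Analysed | Noncentrality | Power, t-test | Power, normal approx. (SD 5.59) | Power, exact Wilcoxon, simulated (SD 5.28) |
|---|---|---|---|---|
| 10 v 10 | 1.325 × √5 = 2.96 | 80.0% | 80.0% | about 76% |
| 9 v 9 | 1.325 × √4.5 = 2.81 | 75.1% | 75.7% | about 69% |
| 8 v 10 | 1.325 / √0.225 = 2.79 | 74.6% | 75.2% | about 70% |
| 8 v 8 | 1.325 × √4 = 2.65 | 69.3% | 70.7% | about 66% |

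The Wilcoxon column (20,000 runs, normal data) is shown because XIV.A uses that test, on the AUC of NPS rather than on BPI.

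**4. How likely such losses are.** No rate is given, so a range is assumed. P(at least 2 of 20 lost) = 1 − (1 − p)^20 − 20p(1 − p)^19, which is 26% at p = 0.05, 61% at 0.10 and 93% at 0.20. If randomisation stays at enrolment, keeping 20 evaluable patients needs 20/0.95, 20/0.90 or 20/0.80, that is 22, 23 or 25 randomised. The documents do not show what share of all losses would fall before closure.

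**5. What removal after unblinding could do.** This is a worst case, with no true effect and SD 5.28 (40,000 runs). Dropping the 1 or 2 highest-pain patients from one arm of 10 shifts the mean difference by about 0.89 or 1.67 points (0.89/7 = 13% and 1.67/7 = 24% of the target difference). The Wilcoxon false-positive rate becomes about 6% or 10%. This sizes the item 8.iii route only. It does not measure the effect of when the draw is made.

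**The case against.** The strongest reply is that the protocol applies its eligibility criteria before allocation. Both intubation criteria are forecasts that can be made before surgery, and no section re-applies them afterwards. A reader might infer that the 48-hour exclusion will be invoked at the end of the operation by a team that is learning the arm, so that early randomisation biases the comparison. The documents do not support that. It is reasonable to think the forecast improves as surgery proceeds, but this is inference, and a conclusion reached before closure would come from a team that is still blinded. This part of the objection stands.

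Second, because XII.5 breaks off, the allocation may already be released late, as blinding until closure implies. That is fair, and the gap in the text is not counted against the plan. But item 4 still places the request at enrolment. If the draw follows then, a patient lost before closure has already taken a place in the list, even if release to theatre comes later.

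Third, the power figures describe any attrition in a trial of 20, rest on a back-solved effect size, and refer to a different outcome from the primary one. This stands too, so they serve as illustration only.

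Fourth, moving the draw does nothing about item 8.iii. That is correct, and it is why the remedy needs an analysis-set rule as well.

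**Conclusion.** The point holds as a cheap improvement in design, not as evidence that the randomised comparison is compromised. Requesting allocation before surgery makes losses before closure count after randomisation, with no offsetting gain visible in the documents. The cost is numbers and block balance. On the illustrative t-test basis, losing 2 of 20 evenly takes 80% power to about 75%, and losing 4 takes it to about 69%. These figures assume two-sided testing, 1:1 allocation, and that the claimed 80% is right. The true loss rate is unknown.

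Losses while the team is blinded should not differ by arm through judgement. Bias could arise only from removals at or after unblinding. Item 8.iii permits these, and the plan states no rule that keeps such patients in the analysis.

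**What to change.** - In XII.4 and XII.5, keep consent, enrolment and baseline BPI before surgery. State that the independent office draws and releases the allocation just before wound closure, once eligibility has been reconfirmed and recorded. Patients lost before that point are reported as enrolled but not randomised.
- In XIV, state that everyone randomised from that point is analysed in the assigned group, and that ending enrolment under item 8.iii does not take a patient out of the analysis. Say how a patient with missing day 3 to 5 scores is handled.

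**Cost.** The change is protocol wording plus one call, or a web log-in if the system allows it, per operation. Independent randomisation staff (or the log-in) and a probe must be available at the end of every case, including those later allocated to control. Electromyography is already planned in both arms. Losses between closure and days 3 to 5 remain, so the second change is needed whether or not the first is adopted.

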8. Termination of enrollment

Patient will be considered to have his/her enrollment terminated:

- i. After the 180-day follow-up visit, or
- ii. If follow-up is lost after several attempts to contact patient, or
- iii. If any medical/surgical/environmental condition develops that would affect or impair primary or secondary outcomes measurements results, or
- iv. If the study is terminated, or
- v. If the patient dies.

9. Termination of Study

- i. End of study period
- ii. If a clinically/statistically significant difference is achieved early during an interim analysis.

XIII. ADVERSE EVENT REPORTING

Patients enrolled in the trial will be informed to report any unwanted effect at any time during the study. Adverse effects of intercostal nerve cryoablation will be made plain to the patients during the screening/enrollment as well as in the informed consent process. Most adverse side effects are injury of the lung or other surrounding organs/tissues, which may happen if cryoablation probe is misplaced to the organ/tissue. This is extremely rare amongst trained and board-certified vascular surgeons. All the surgeons involved in our study have been extensively trained on the cryoablation technique required for appropriate use. Other adverse effects include

allodynia like-pain after the degeneration of the affected nerve is reported after cryoablation of the nerve, but this is often associated with thoracotomy procedure and not specific to the cryoablation. Safety monitoring will include assessment of:

- i. Adverse Effects (AE)
- ii. Vital Signs
- iii. Wound healing status
- iv. Scarring
- v. Cardiac monitoring

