All items above will be closely monitored in a continuous manner, as part of our standard postoperative care. Any abnormalities found will be promptly assessed and described in the patient's medical records. Once the patient is discharged it is very unlikely that any of the study drugs or procedure will cause any abnormalities. Despite this fact, patients will be asked to contact the hospital in case they feel anything unusual. Definitions and examples of the standard or known adverse events associated with cryoablation is tingling, burning sensation, etc., will be presented to the patient for reference. Patients will be also assessed on the above items on their postoperative clinic visits. In addition, emergency contact information of the office in order to speak to someone regarding documentation of these adverse events will be provided. If need be, an immediate unscheduled visit shall be arranged if the patient so desires. The PI will review AE as they occur, changes to the study design or drug use will be determined on an ongoing basis.

XIV. STATISTICAL ANALYSIS PLAN

A. Primary Outcomes

NPS measures will be plotted for each subject over the initial third to fifth postoperatively and the area under the curve (AUC) integrated to produce a cumulative numeric pain score. The primary endpoint will be measured by a statistical comparison of AUC between the groups, using a Wilcoxon rank-sum test. Randomization is expected to balance the groups with respect to preoperative risk factors.

B. Secondary Outcomes

Cumulative dose of opioid medication will be assessed as the sum of morphine doses dispensed by PCA pump during the admission. In addition, we will evaluate the amount of opioid usage using morphine milligram equivalences.²² This will be compared by unpaired t test. We will also evaluate for the opioid prescription need at the time of discharge, and will be compared by chi-square test. Length of hospital stay will be transformed to log scale to normalize the distribution if necessary and will be compared between groups by an appropriate unpaired statistic. Attainment of physical therapy goal that justifies discharge from inpatient physical therapy within 72 hours will be assessed by an appropriate contingency table test.

C. Sample Size Determination

This is a pilot study to prove the feasibility of intercostal nerve cryoablation in patients undergoing the descending/thoracoabdominal aortic aneurysm repair with thoracoabdominal incision.

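### The protocol allows an early stop on a significant interim difference but sets no looks, endpoint, boundary or alpha adjustment, so control of alpha <0.05 is not shown

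*Combined protocol and SAP*

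**What the plan says.** Section XII.9 (Termination of Study) gives two grounds for ending the study: the end of the study period, and "If a clinically/statistically significant difference is achieved early during an interim analysis".

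Two other places show that this is intended. The synopsis and section XII call the design sequential. Section XVI (Study Timeline) bases its recruitment estimate partly on "drop-outs and withdrawal, and interim analyses we estimate recruitment of our sample size will take 6 months".

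The analysis plan is silent on the matter. Section XIV.A compares the area under the curve (AUC) of the Numeric Pain Scale (NPS) between groups "using a Wilcoxon rank-sum test", with no mention of an interim test. Section XIV.C states that 20 subjects detect a seven-point fall in cumulative three-day Brief Pain Inventory (BPI) score "with 80% power at alpha <0.05". That is the only significance level in the document, and its sidedness is not given.

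For follow-up, section XII.8 ends a patient's enrollment on several grounds, one being "If the study is terminated, or". The timeline plans "Follow-up up to 180 days from the last patient enrolled".

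**The concern.** The rule can end the trial, yet it cannot be applied as written. Section VII lists three primary outcome measures (NPS AUC, BPI, satisfaction), section XIV.A tests the first, and section XIV.C powers on the second. Nothing says which of them triggers a stop, at what threshold or after how many patients. The slash also leaves open whether an undefined clinical difference could stop the trial alone.

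Two things are at stake. The first is the error rate: section XIV.C quotes a level, and repeated testing at that level exceeds it. The second is the estimate: section VI makes a larger randomized study conditional on this pilot showing efficacy, and trials that stop early on a large difference overstate it.

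A smaller matter is what happens to patients already enrolled. Day-30 and day-180 BPI and satisfaction scores are listed under the primary outcome measures, and an early stop might end their collection.

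**Working it through.** **Inputs.** From the plan: 20 patients, Wilcoxon rank-sum test, alpha <0.05, 80% power, 7-point effect. Assumed: two-sided testing; 10 per arm (consistent with the 10 probes in section XVIII); every look schedule; every SD.

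**1. The plan's own figure.** The 80% power cannot be reproduced because no SD is given. A two-sided t-test with 10 per arm has 80% power at a standardized difference of 1.325, so the implied SD is 7 / 1.325 = 5.28. At that SD the Wilcoxon test has about 75.6% power with no interim look.

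**2. One look at 5 v 5, each test at 0.05.**
- Interim: there are C(10,5) = 252 equally likely arrangements under the null. Four of them have U ≤ 2, so the two-sided size is 2 × 4 / 252 = 3.17%. Including U = 3 (seven arrangements) gives 14 / 252 = 5.6%, which is too large.
- Final: at 10 v 10 the critical value is U ≤ 23, with exact size 4.33%.
- The chance of rejecting at either test is at most 3.17 + 4.33 = 7.50%. Because the tests share patients, simulation gives 6.5%.

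**3. Other schedules** (simulated null trials, exact Wilcoxon p, balanced arms, no ties).

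| Interim looks (total patients) | Type I error |
|---|---|
| none | 4.3% |
| one, at 8 / 10 / 12 / 14 / 16 / 18 | 6.5 / 6.5 / 6.9 / 6.3 / 6.8 / 5.6% |
| two, at 14 and 18 | 7.1% |
| two, at 8 and 14 | 8.1% |
| three, at 8, 12 and 16 | 9.8% |
| six, at every even count from 8 to 18 | 11.2% |

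Over all balanced schedules with looks at even counts from 8 to 18, one look gives 5.6–7.0% and two to six looks give about 7–11%. Simulation scatter puts the ends of the latter range at 7.1–7.2% and 11.2–11.3%.

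**4. Balance and ties.** Allocation uses a "computer generated block randomization sequence/list" with no block size, so a look may be unbalanced. At 10 patients the error is 7.1% for 4 v 6 and 6.8% for 3 v 7. The AUC is built from six integer scores, so ties are likely. In simulated integer scores (assumed patient mean 5 or 7, between-patient SD 1–2, within-patient SD 1–1.5), the tie-exact test gives 5.0–5.1% with no look and 7.6–7.8% with one at 5 v 5.

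**5. Size of the estimate.** The plan's only effect size is on the BPI scale, while its Wilcoxon test is specified for the NPS AUC. This step applies that test to untied normal data on the BPI scale and is only an illustration. The true effect is 7 and any look is at 5 v 5.

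| SD (assumed) | Mean effect in significant trials: no look | one look at 0.05 | Pocock 0.0294 at both tests |
|---|---|---|---|
| 5.28 | 7.9 | 8.5 | 8.6 |
| 8 | 10.1 | 11.0 | 11.2 |

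At SD 5.28 with an unadjusted look, the excess over 7 is 8.5 − 7 = 1.5. Of this, 7.9 − 7 = 0.9 comes from selecting significant trials and 8.5 − 7.9 = 0.6 from the look. About 35% of trials stop early, with a mean estimate of 9.9.

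**6. Follow-up.** Suppose 20 patients are spaced evenly over 180 days, one every 9 days. The tenth is operated on at day 90 and reaches postoperative day 5 at day 95. Patients operated on by day 65 are past day 30: seven of ten (7 × 9 = 63). None has reached day 180.

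**The case against.** The strongest reply is that this is a 20-patient pilot meant to gather preliminary data. One unadjusted look moves the error from 4.3% to about 6.5%, and adds about 0.6 points to an overestimate that comes mostly from significance selection. That stands, and it limits the severity. It does not remove the point: the protocol states an alpha, a power and an efficacy stop, and ties the next trial to demonstrated efficacy.

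It is also fair that no schedule is stated, so no single inflation figure belongs to this trial. A reader might infer that the plan as written has an inflated error rate. The documents do not go that far: they do not say that each look uses 0.05, only that no other level is given.

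Two further readings are tempting but unsupported. The timeline's sentence "Once the follow-up of all enrolled participants is finished, data will be analyzed and published" might seem to contradict interim analyses. It reads naturally as the final analysis before publication and does not exclude earlier looks. Section XII.8 might likewise seem to contradict the 180-day follow-up. It is a contingency beside an estimate of the planned course, so only a clarification is needed. Section XIV also names no test of day-30 or day-180 data, so the loss would not affect any stated test.

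**Conclusion.** The point holds. The protocol permits an efficacy stop that the analysis plan does not define, so control of the stated level is not shown. It fails under every balanced schedule examined if each look is tested at two-sided 0.05: about 5.6–7.0% with one interim look and 7–11% with two to six, against 4.3% with none. These figures assume 10 v 10 at the end and no ties; imbalance or ties at a look at 10 patients give 6.8–7.8%.

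The added overestimate is modest, about 0.6 points on a true 7 at an assumed SD of 5.28, and should not be presented as the main source of bias. The correction is needed before any data are looked at. In a pilot of this size it is not critical.

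**What to change.** **Preferred.** Delete the interim stop in XII.9, the word *sequential* in the synopsis and section XII, and the mention of interim analyses in section XVI. State one final primary analysis at two-sided 0.05. Keep the investigator's safety review (sections XIII and XVII) as a separate item. This is a wording change; the cost is giving up an early efficacy stop within a six-month enrollment.

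**If a look is kept.** Name one endpoint, one time for the look and one boundary, and remove *clinically* as a stand-alone trigger. Define the boundary on the exact permutation p-value for the observed group sizes and ties. An example is Pocock's nominal 0.0294 at both tests:
- With a look at 5 v 5, overall error is about 4.0% without ties and 4.2% with ties. With 4 v 6 or 3 v 7 it is 4.2–4.3%.
- Power for 7 points falls from about 76% to 71% at SD 5.28, from 94.0% to 91.7% at SD 4, and from 41.3% to 36.3% at SD 8.
- The overestimate is not reduced (8.6 against 8.5 unadjusted and 7.9 with no look). An estimate after an early stop should therefore carry a bias adjustment or an explicit caution.

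An O'Brien–Fleming boundary for two equal looks needs about 0.005 at the first. The smallest two-sided p at 5 v 5 is 2 / 252 = 0.0079, so that look could never stop the trial.

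**If an early stop remains possible**, say in XII.8 whether patients already enrolled still complete the day-30 and day-180 assessments.
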